1.0 Objectives

1.1 *Describe the purpose, specific aims, or objectives.*

We propose to study the effect of Acthar® on recovery from cognitive relapses in multiple sclerosis (MS). Cognitive relapses are acute clinical declines in concentration, memory, working memory or increased fatigue. Cognitive relapses may also be detected by the presence on brain MRI of new active supratentorial Gad enhancing lesions. We will use well-validated, objective metrics to evaluate cognitive changes following treatment with a 5-day course of Acthar® over three months in patients showing cognitive relapses in MS. To account for the possible practice effects of cognitive testing over a three-month period, we will compare the results to a matched sample of MS patients who are clinically stable.

1.2 *State the hypotheses to be tested.*

The primary hypothesis of the study is that due to enhanced melanocortin response, Acthar will facilitate recovery from cognitive changes occurring during cognitively focused relapse, and that patients treated with Acthar will return to baseline following treatment.

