11.0 Data Management

11.1 Describe the data analysis plan, including any statistical procedures.

Data will be processed by trained research assistants blind to study hypotheses. Analysis will be conducted using SPSS 22.0. Analysis strategy will be repeated measures analysis of variance where baseline, day 0 and day 90 scores are compared. Analysis of variance will be used

University at Buffalo Institutional Review Board (UBIRB)

Office of Research Compliance | Clinical and Translational Research Center Room 5018
[name]
UB Federalwide Assurance ID#: FWA00008824

PROTOCOL TITLE: Effects of adrenocorticotropic hormone (Acthar gel®) on recovery from cognitive relapses in MS.

to compare the magnitude of change between day 0 and 90 between the MS patients treated with Acthar and the previously collected controls. Analysis of variance will also be used to compare the magnitude of cognitive recovery after corticosteroid treatment to that after Acthar treatment.

The difference between the means at Day 0 and Day 90 will be used to calculate Cohen's d for each group. To facilitate analysis, all data will be normalized using a large previously published control sample.¹³ All tests will be performed based on an alpha of 0.05. Net effect sizes removing estimated practice effects will be calculated using Cohen's d.

11.2 Provide a power analysis.

The selection of 30 as the target enrollment is based on the previously completed study of 25 relapsing and 25 stable MS patients. Five additional patients are planned in order to increase the power of subsequent analyses. A power analysis based on the observed effect of corticosteroids in the relapsing group of $d = .56$ with 30 participants will be powered $>85\%$ to detect effects of a moderate magnitude from Acthar.

11.3 Describe the steps that will be taken to secure the data (e.g., training, authorization of access, password protection, encryption, physical controls, certificates of confidentiality, and separation of identifiers and data) during storage, use, and transmission.

All clinical and neurometric assessments will be conducted under the supervision of the PI. All members of research team will complete relevant training programs and courses, including but not limited to: HIPAA, CITI and GRP.

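### The within-group, Acthar-versus-stable and net Cohen's d analyses leave natural relapse recovery in the Acthar estimate, so they cannot by themselves support the claim that Acthar facilitates recovery

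*Combined protocol and SAP*

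**What the plan says.** The primary hypothesis in section 1.2 has two parts. One is causal: "Acthar will facilitate recovery from cognitive changes occurring during cognitively focused relapse". The other is descriptive: "patients treated with Acthar will return to baseline following treatment".

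Section 1.1 gives the stable group one task: "To account for the possible practice effects of cognitive testing over a three-month period, we will compare the results to a matched sample". Section 7.1 describes an open-label study with a stable MS control group. Under section 9.2, only patients who accept Acthar treatment are approached, so no relapsing patient in the study goes untreated.

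Section 11.1 plans four things:

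- A within-group analysis: "Analysis strategy will be repeated measures analysis of variance where baseline, day 0 and day 90 scores are compared".
- An analysis of variance "to compare the magnitude of change between day 0 and 90 between the MS patients treated with Acthar and the previously collected controls".
- A further analysis of variance to "compare the magnitude of cognitive recovery after corticosteroid treatment to that after Acthar treatment". Sections 2.2 and 2.3 also declare this comparison.
- A standardised effect: "Net effect sizes removing estimated practice effects will be calculated" using Cohen's d.

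Section 11.2 describes the power as being "to detect effects of a moderate magnitude from Acthar". Section 2.3 says, on limited evidence, that some cognitive deficits seen in acute relapse may reverse. It gives no size and does not say whether the patients concerned were treated.

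**The concern.** To say that Acthar facilitates recovery, one needs an estimate of how relapsing patients would have done without it. Stable patients cannot supply that, because they have no relapse deficit to lose. Their change over 90 days estimates practice, which is the job section 1.1 gives them.

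If relapse deficits resolve partly by themselves, an inert drug could produce a larger gain in the Acthar group than in the stable group and a positive net d. The plan does not say how such a result will be worded. Read against section 1.2, it would look like confirmation of the primary hypothesis, and the phrasing in 11.2 already attributes the effect to the drug.

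**Working it through.** **What each contrast contains.** Let A be the Acthar effect, S the corticosteroid effect, N natural relapse recovery and P practice, all as mean change from day 0 to day 90. Take P as equal across groups and N as equal in the two relapsing groups.

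| Contrast in 11.1 | Contains |
|---|---|
| Within Acthar group | A + N + P |
| Acthar minus stable | (A + N + P) − P = A + N |
| Net Cohen's d, practice removed | A + N, standardised |
| Acthar minus corticosteroid | (A + N + P) − (S + N + P) = A − S |

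Only the last row is free of N, and only if the two relapsing cohorts are comparable.

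**The plan's own power figure.** Inputs from 11.1 and 11.2: n = 30, d = 0.56, alpha 0.05. Two-sided testing is assumed because sidedness is not stated, and d is read as SD-of-change units. For a within-group change:

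- Normal approximation: Φ(0.56 × √30 − 1.96) = Φ(3.067 − 1.96) = 86.6%.
- Noncentral t, 29 df: 84.2%.

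So the stated power above 85% is reproduced to within about a point as a test of A + N + P. A two-group comparison of change with the same d does not reproduce it (noncentral t: 56.9% at 30 v 30, 52.8% at 30 v 25).

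**Inert drug, A = 0, Acthar versus stable.** N is an assumed range. Section 23 gives 30 relapsing and 30 stable patients, but 11.1 refers to controls already collected and 11.2 to an earlier study with 25 stable patients, so both sizes are shown. The noncentrality is N ÷ √(1/n₁ + 1/n₂). The divisor is √(2/30) = 0.258 for 30 v 30 and √(1/30 + 1/25) = 0.271 for 30 v 25.

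| Assumed N (SD of change) | Noncentrality, 30 v 30 | Significant, 30 v 30 | Significant, 30 v 25 |
|---|---|---|---|
| 0 | 0 | 5% | 5% |
| 0.1 | 0.39 | 6.7% | 6.5% |
| 0.2 | 0.77 | 11.9% | 11.2% |
| 0.3 | 1.16 | 20.8% | 19.3% |
| 0.5 | 1.94 | 47.8% | 44.2% |
| 0.56 | 2.17 | 56.9% | 52.8% |

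The smallest observed difference that reaches significance at 30 v 30 is 2.00 × 0.258 = 0.52 SD of change; at 30 v 25 it is 2.01 × 0.271 = 0.54. The within-group test is more exposed: with A = 0 and no practice effect, N of 0.1, 0.2 or 0.56 gives significance in 8.3%, 18.5% or 84.2% of trials.

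**Corticosteroid contrast.** If A = S and the cohorts are comparable, the false-positive rate is 5% whatever N is. If the comparator is the 25 relapsers of the earlier study (an assumption), then at 30 v 25 power is 11.2%, 30.5% or 52.8% for a true Acthar advantage of 0.2, 0.4 or 0.56 SD. An advantage of about 0.77 SD is needed for 80% power. The 95% confidence interval half-width is about 0.54 SD.

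**The case against.** The best reply is that section 11.1 does contain a relapsing comparator. A reader might infer that nothing in 11.1 can bear on facilitation; the documents do not support that. Natural recovery drops out of the corticosteroid contrast in principle. An advantage over an active treatment needs no untreated arm to count for something, provided corticosteroids do not slow recovery, and sections 2.2 and 2.3 cite randomised evidence that they promote stabilisation or improvement after exacerbations. This stands. The support is limited because the comparison is not described as randomised, matched or adjusted, and power is low. If recovery is merely similar, A − S is near zero; the plan gives no non-inferiority margin, and the result would not show that A is above zero.

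A second reply is disclosure. The plan says it is open-label, says what the stable controls are for, and describes the net d as having practice removed; 11.1 does not call that net d a drug effect. This is fair and lowers the severity, but it does not supply the missing limit on the causal hypothesis in 1.2.

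A third reply is that the illustration rests on assumed recovery. That also stands. The top value, 0.56, is the change seen after corticosteroids, so using it credits the whole of that change to nature. At 0.1 the excess over 5% is under two percentage points.

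A reader might also infer a sizeable regression-to-the-mean bias, since entry uses an SDMT decline. The documents do not support a figure. Section 9.2 repeats the SDMT in the full battery, which suggests the battery score is day 0. With independent errors that score carries no such bias. Percentages for using the screening score depend heavily on the true drop assumed.

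**Conclusion.** The point holds for the within-group analysis, the Acthar-versus-stable contrast and the net Cohen's d. None of them separates an Acthar effect from natural relapse recovery, so none can by itself support the facilitation part of section 1.2. The return-to-baseline part is unaffected as a description.

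The corticosteroid contrast is the exception: a clear Acthar advantage would give limited relative support, and parity would not show efficacy.

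The size is conditional. With an inert drug the stable contrast is significant in 7% to 57% of trials for assumed recovery of 0.1 to 0.56 SD of change at 30 v 30. This rests on two-sided 0.05, equal practice in both groups, equal SDs, and d in SD-of-change units. It shows what is possible, not what is likely. The open-label design is not itself the fault; the fault is a causal hypothesis without a stated limit on what these contrasts can show.

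**What to change.** 1. In 1.2 and 11.1, add: *A larger day 0–90 gain than in stable controls, or a positive net Cohen's d, will be reported as recovery after Acthar beyond practice. It does not separate an Acthar effect from natural relapse recovery and will not by itself be reported as showing that Acthar facilitated recovery. The corticosteroid comparison is non-randomised and gives relative evidence only: an Acthar advantage gives limited support, and similar recovery does not show efficacy.* In 11.2, describe the powered quantity as change after Acthar. Keep return to baseline as a descriptive aim served by the repeated-measures analysis.

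2. Minor: in 11.1, name the SDMT given in the full battery (section 9.2) as the day-0 score, not the screening score used for entry.

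3. Separate point: the SDMT entry rules in 3.1 (1a) and 9.2 do not fit the stated purpose of confirming decline. The first asks for a change above minus 3 raw points; the second accepts a decline of 3 points or fewer. Read literally, this wording admits patients with little or no decline. The passages must be reconciled.

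These are wording changes with no new patients or visits. The price is a narrower causal claim.

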11.7 Where and how data or specimens will be stored?

Neuropsychological testing data will be kept in a locked room and in a locked cabinet.

11.8 How long the data or specimens will be stored?

De-identified data will be stored for the remainder of the study and according to appropriate legal guidelines regarding retention of records. De-identified data may be stored indefinitely for future studies, not yet determined.

11.9 Who will have access to the data or specimens?

Trained staff under [name] (Primary Investigator) directly involved in the conduct of this study will have access to data. Identifiable data will not be released to any outside sources. Investigator will refer to the Clinical Trial Agreement for details regarding the disclosure of study results.

11.10 Who is responsible for receipt or transmission of the data or specimens?

Identifiable data will not be released to any outside sources. Investigator will refer to the Clinical Trial Agreement for details regarding the disclosure of study results.

11.11 How data and specimens will be transported?

N/A

12.0 Provisions to Monitor the Data and Ensure the Safety of Subjects

12.1 Describe the plan to periodically evaluate the data collected regarding both harms and benefits to determine whether subjects remain safe.

Patients will be assessed for general safety and asked about potential adverse events on day 7 and day 30.

University at Buffalo Institutional Review Board (UBIRB)

Office of Research Compliance | Clinical and Translational Research Center Room 5018
[name]
UB Federalwide Assurance ID#: FWA00008824

PROTOCOL TITLE: Effects of adrenocorticotropic hormone (Acthar gel®) on recovery from cognitive relapses in MS.

12.2 Describe what data are reviewed, including safety data, untoward events, and efficacy data.

Data being reviewed will be patient self-report of general safety and potential adverse events.

12.3 Describe how the safety information will be collected (e.g., with case report forms, at study visits, by telephone calls with participants).

Safety information will be collected at each study visit and via telephone on day 7 and day 30.

12.4 Describe the frequency of data collection, including when safety data collection starts.

Neuropsychological and clinical outcome data will be collected at day 0 and day 90. Information on safety of patient will be collected via telephone on day 7 and day 30.

12.5 Describe who will review the data.

Designated, trained staff under [name] (Primary Investigator) will review neuropsychological, clinical outcome, and safety data. A Data and Safety Monitor (DSM) will also review recruitment, visit schedules, missed visits, patient compliance, demographics, outcomes, and adverse events.

12.6 Describe the frequency or periodicity of review of cumulative data.

Neuropsychological, clinical outcome and safety data will be reviewed at each data collection and additionally by the Data and Safety Monitor (DSM) upon the enrollment of every 10 participants and/or in the event that any adverse, serious or non-serious event occurs, and/or every 6 months or more frequently if deemed necessary.

12.7 Describe the statistical tests for analyzing the safety data to determine whether harm is occurring.

N/A

University at Buffalo Institutional Review Board (UBIRB)

Office of Research Compliance | Clinical and Translational Research Center Room 5018
[name]
UB Federalwide Assurance ID#: FWA00008824

PROTOCOL TITLE: Effects of adrenocorticotrophic hormone (Acthar gel®) on recovery from cognitive relapses in MS.

12.8 Describe any conditions that trigger an immediate suspension of the research.

N/A

13.0 Withdrawal of Subjects

13.1 Describe anticipated circumstances under which subjects will be withdrawn from the research without their consent.

Circumstances that could possibly lead to the withdrawal of a subject without his or her consent would be if continuation of treatment with Acthar was no longer in the patient's best interest, based on treating clinician judgment. The treating clinician may remove subjects from the study at any time should he/she feel it is no longer in the subject's best interest or if the patient is non-compliant with study procedures.

13.2 Describe any procedures for orderly termination.

In the event of early termination/withdrawal from the study, an in-person exit interview will be conducted by the PI, treating clinician or trained members of the research team.

13.3 Describe procedures that will be followed when subjects withdraw from the research, including partial withdrawal from procedures with continued data collection.

Participation in this study is voluntary. Patients being treated with the study medication may refuse to participate without penalty and such refusal will not prejudice future treatment or benefits at the UBMD Neurology. Patients will be free to discontinue participation in the study at any time without fear of penalty or loss of medical care or loss of any benefits to which you may otherwise be entitled. If a subject chooses to withdraw from the study, the data collected up to the time of withdrawal will continue to be used, but the subject will no longer be contacted and no further data will be collected.

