7.0 Study Timelines

7.1 *Describe the duration of an individual subject's participation in the study.*

This is a prospective, open-label study of Acthar administered as treatment for an acute cognitive relapse. Primary and secondary endpoints will be collected prior to Acthar administration and at 3-month follow-up. Comparison will be made to a stable MS control group.

7.2 *Describe the duration anticipated to enroll all study subjects.*

Enrollment of all study participants is expected to take 4 years (48 months).

7.3 *Describe the estimated date for the investigators to complete this study (complete primary analyses)*

Completion of this study, including primary analysis, is expected within 5 years.

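### Section 13 does not separate stopping Acthar from leaving the study, so treated patients removed by the clinician can be lost from the day-90 analysis

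*Combined protocol and SAP*

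**What the plan says.** Section 7.1 sets the design: "This is a prospective, open-label study of Acthar administered as treatment for an acute cognitive relapse". Section 9.2 gives the course as 5 days, extendable to 2 weeks depending on clinical response or adverse events. Section 12.4 places the neuropsychological and clinical outcomes at day 0 and day 90 only.

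Section 13.1 answers a question about withdrawal from the research. It says that possible grounds for "the withdrawal of a subject without his or her consent would be if continuation of treatment with Acthar was no longer in the" best interest of the patient, on the treating clinician's judgment. It continues: "The treating clinician may remove subjects from the study at any time", on best-interest grounds or for non-compliance with study procedures.

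What follows depends on who decides:

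- **Any early termination or withdrawal (13.2):** "In the event of early termination/withdrawal from the study, an in-person exit interview will be conducted by the PI", the treating clinician or trained staff. No cognitive test is named.
- **A subject who chooses to withdraw (13.3):** "the subject will no longer be contacted and no further data will be collected", although "the data collected up to the time of withdrawal will continue to be used". The prompt for 13.3 asks about partial withdrawal with continued data collection. The response offers no such option.

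Section 11.1 plans "repeated measures analysis of variance where baseline, day 0 and day 90 scores are compared", an analysis of variance on the day 0 to day 90 change, and Cohen's d from the day 0 and day 90 means. It states no analysis population and no method for missing scores. Section 11.2 explains the step from 25 to 30 patients: "Five additional patients are planned in order to increase the power of subsequent analyses". No allowance for loss is given.

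**The concern.** The decision to stop the drug falls within the first two weeks, while the outcome is read about eleven weeks later. Section 13.1 lets the first end the second, and the person deciding knows the treatment. Nothing in section 13 keeps a patient who stops Acthar in follow-up to day 90.

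If removal is unrelated to recovery, the cost is precision only. If it tends to follow a poor response, the patients left at day 90 are a favourable selection of those treated, and their mean change overstates the recovery of all treated patients. The comparison with stable controls shifts the same way, because controls receive no Acthar and cannot be removed on that ground. A day-90 score that was never collected cannot be recovered at analysis.

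**Working it through.** **Step 1: does the removed patient leave the analysis?** The day 0 to day 90 change needs both scores. A standard repeated measures analysis of variance on three time points keeps only cases with all three. Retaining data gathered before withdrawal (13.3) does not help, because those data hold no post-treatment outcome. So the patient is left out of both analyses.

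**Step 2: reproduce the plan's power figure.** Inputs from 11.1 and 11.2 are n = 30, d = 0.56 and alpha 0.05. Sidedness is not stated, so two-sided is assumed. Section 11.2 does not say what SD underlies d, so it is taken in units of the SD of change.

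- Paired test, normal approximation: Φ(0.56 × √30 − 1.96) = Φ(1.107) = 86.6%.
- Paired test, noncentral t: 84.2%.

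Both lie within 2 points of the stated figure of more than 85%, so it reproduces as a within-group test. A 30 versus 30 comparison of change gives 56.9%. The paired test is therefore used below.

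**Step 3: size of the overstatement.** The documents give no removal rate, so the number removed, k, is assumed. Let q = k/30, let the remaining patients gain g = 0.56, and let the removed patients have gained nothing. The mean of all treated is (1 − q)g, the analysis shows g, and the overstatement is qg.

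| k removed of 30 | Mean gain, all treated | Overstatement (SD) | Relative to all treated | Paired power at 30 − k |
|---|---|---|---|---|
| 1 | 0.541 | 0.019 | 3.4% | 82.9% |
| 2 | 0.523 | 0.037 | 7.1% | 81.5% |
| 3 | 0.504 | 0.056 | 11.1% | 80.0% |
| 6 | 0.448 | 0.112 | 25.0% | 74.8% |

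The power column takes loss as unrelated to outcome. The row for 6 is an outer case.

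**Step 4: other assumptions about who is lost.** In general the overstatement is q × δ, where δ is the gap between the mean of those kept and the mean of those lost. For k = 3 (q = 0.1), δ of 0.5 to 1.0 SD gives 0.05 to 0.10 SD.

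In a simulation of 200,000 trials, the k patients lowest on a variable correlated r with the day-90 change were removed:

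- r = 0.3: shifts of 0.022, 0.039 and 0.056 SD for k = 1, 2 and 3.
- r = 0.5: shifts of 0.035, 0.066 and 0.093 SD.

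The extreme is losing exactly the three worst responders, which shifts the mean by about 0.19 SD.

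**Step 5: put the size in context.** For k = 3 and zero gain, with an SD of change of 1 in each group:

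- Within group: SE = 1/√27 = 0.192, so 0.056 SD is 0.29 of a standard error.
- Against 30 stable controls: SE = √(1/27 + 1/30) = 0.265, so 0.056 SD is 0.21 of a standard error.

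**The case against.** The strongest reply is that the documents do not make poor response a ground for removal. Section 13.1 says could possibly, and names best interest and non-compliance. Section 9.2 ties clinical response to how long Acthar is given, not to staying in the study. No cognitive test is scheduled between day 0 and day 90, so a clinician who stops the drug early has no scheduled follow-up score to act on and may well be acting on tolerability. The one removal stated as certain is for pregnancy (14.1), which has no evident link to cognitive recovery. The independent monitor also sees missed visits, compliance and outcomes (11.4, 12.5). All of this stands. It makes outcome-related removal possible rather than expected, and it keeps the likely effect small. The monitor makes losses visible but does not recover scores.

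Three stronger readings are tempting, and the documents do not support them.

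- **That patients who switch treatment are removed.** Section 20.5 lets the clinician treat relapses as needed and says nothing of removal. A retreated patient may stay and be tested at day 90.
- **That 13.3 forbids a day-90 test for anyone removed.** Its bar on further data covers subjects who choose to withdraw. For removal by the clinician there is only the exit interview in 13.2, and silence otherwise.
- **That the comparison with corticosteroid patients must favour Acthar.** Losses in that earlier group are not given. If those 25 are completers too, similar selection could partly cancel the shift.

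Recording of other medication is not at issue either: sections 8.1, 9.2 and 9.3 provide for it.

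**Conclusion.** The point holds as a weakness in the plan's wording that is cheap to repair. Followed as written, section 13 permits treated patients to be lost to the day-90 analysis for reasons connected with their treatment, and nothing in section 11 deals with that. The direction is towards overstating Acthar, within the group and against stable controls, only if removal is related to poor response. Against the earlier corticosteroid group the direction is unknown.

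The size cannot be established from the documents. On the assumed case of 1 to 3 removals with no gain, it is 0.02 to 0.06 SD on a gain of 0.56, or less than a third of a standard error, plus a fall in paired power from 84% to 80% at 27 patients. These figures rest on assumed removal counts, an assumed zero gain, two-sided testing, and d in SD-of-change units. With few removals the effect may be negligible.

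**What to change.** In 13.1, 13.2 and the consent form, state that stopping Acthar, non-compliance or other relapse treatment does not by itself end participation. Such patients are still asked to attend the day-90 assessment, unless they withdraw consent or attending would be unsafe.

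In 11.1:

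- Include every treated patient with a day-90 score, whether or not the Acthar course was completed.
- Report how many have no day-90 score, with reasons.
- Give one sensitivity result that assigns those patients no gain.

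A mixed model using all available scores, and an analysis that sets aside retreated patients, are optional. With a single post-treatment score the first adds little for a patient who lacks it, and the second answers a different question.

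The cost is a few sentences. No visit is added and clinical decisions are unchanged. Some removed patients will decline the visit, scores taken after other treatment reflect both treatments, and the no-gain result is conservative.
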